to exercise or weight loss only interventions. If we find minimal changes in insulin sensitivity with either intervention used in isolation, we will move to a combined intervention. Different degrees of success with the interventions are important to provide a spread in the data for changes in localized lipids and insulin sensitivity. An alternative approach would be to provide food for subjects to consume prior to both insulin clamps. We excluded this design because of the possibility of changing muscle lipid species and localization with changing dietary patterns. If individuals cannot maintain their weight within 2kg of starting weight in the exercise only intervention, they will be removed from the study. Our focus in this proposal is on DAG and sphingolipids, however, we will also measure changes in triglyceride, long chain acyl-CoA, and phosphatidic acid to determine other lipids related to changes in insulin sensitivity and/or cellular signaling. If there are no changes in PKC, we will evaluate changes in non-PKC DAG targets such as PKD and RasGRP1/4 to determine if these less studied DAG targets relate to insulin resistance.

Our typical muscle biopsy yield after removal of extra-muscular lipid, is approximately 160mg wet weight, and the tissue required for the assays in this project is 135mg wet weight, allowing all assays to be performed on the majority of biopsies. If muscle yield is limiting, we will prioritize analysis in the following order: subcellular fractionation (50mg) >western blot (15mg) >mitochondrial respiration (25mg) >PP2A activity (10mg) >PKC activity (35mg). We will also evaluate changes in other mitochondrial/ER lipids related to changes in mitochondrial function. In addition to those lipids listed under aim 1, we will also measure cardiolipin content as well as composition.

F. Data Analysis Plan:

Aim 1: Our statistical methods are rigorous with an a priori statistical analysis plan to test our hypothesis in an unbiased manner, and power analysis based on our own preliminary data. Prior to analysis, data will be analyzed for normality, and any non-normally distributed variables will be log-transformed for use in analytic models. Correlations between the change in sarcolemmal DAG and sphingolipid species and the change in insulin sensitivity will be performed using Pearson's correlation coefficients in the entire study group (n=51). Then, data comparing changes in sarcolemmal DAG and sphingolipid species to changes in insulin sensitivity before and after the intervention will be analyzed using a one-way Analysis of Variance (ANOVA) to examine overall differences between the intervention groups, and using Tukey's procedure to make pair-wise comparisons (e.g control vs. exercise, control vs. diet only) while adjusting for multiple comparisons. Changes in individual DAG and ceramide species will be examined using the Benjamini Hochberg procedure to limit false discoveries (62), and then Principal Component Analysis (PCA) will be used to examine groups of DAG and ceramide species (13). Analyses will be conducted using SAS statistical software ver. 9.4 (Cary, NC). The power analysis is based on changes in sarcolemmal lipids assuming there will be no significant changes in the control intervention. With an overall n of 51, we will have 92% power to detect a Pearson correlation coefficient similar to our preliminary data (Figure 2B, r= -0.45), and 80% power to detect a correlation coefficient as small as -0.38. Pilot data showed sarcolemmal C18:0 ceramide decreased 0.041 ng/ug protein with a SD of .02 after the combined intervention. With an n of 17/group we will have 84.6% power to measure a similar change in sarcolemmal DAG and sphingolipids for individual group comparisons using the Tukey procedure. The type 1 error rate (alpha) will be set at 5% for all comparisons.

Aim 2: Our statistical methods are rigorous with an *a priori* statistical analysis plan to test our hypothesis in an unbiased manner, and power analysis based on our own preliminary data. Data will be analyzed for normality, and any non-normally distributed variables will be log-transformed for use in analytic models. Correlations between the change in mitochondrial/ER DAG and sphingolipid species and the change in insulin sensitivity, mitochondrial respiration, ROS production, acyl-carnitine species, and ER stress will be performed using Pearson's correlations coefficient in the overall study group. Data comparing changes in mitochondrial/ER DAG and sphingolipid species to changes in insulin sensitivity and parameters of mitochondrial respiration between groups before and after the intervention will be analyzed using a oneway ANOVA (SAS statistical software ver. 9.4, Cary, NC). If overall differences are observed by group then individual group comparisons will be made using Tukey's procedure, which corrects for family-wise error rates. Changes in individual DAG and ceramide species will be examined using the Benjamini Hochberg procedure to limit false discoveries, and changes in groups of DAG and ceramide species will be examined using PCA as described in Aim #1. Our power analysis is based on our preliminary data for the change in mitochondrial ceramide and DAG species after the pilot intervention shown in Figures 8 and 10, and assuming there will be no significant changes in the control intervention. With an overall n of 51, we will have 99% power to detect a Pearson correlation coefficient as large as that observed in our preliminary data (Figure 7B, r= -0.44), and we will have 80% power to detect a correlation coefficient as small as -0.38. With an n of 17/group, we will have 95% power to measure a similar change in mitochondrial DAG and sphingolipids as we have observed in our pilot data after the weight loss or exercise interventions using pairwise comparisons in ANOVA models using the Tukey procedure. The type 1 error rate (alpha) will be set at 5% for all comparisons.

Data analysis plan for secondary data points regarding sleep component of the study: Sleep duration and markers of sleep quality will be obtained from Actiwatch recordings and scored using the provided Actiware Software. Data are collected from one week preceding the baseline clamp study visit and again from one week preceding the post-intervention clamp study visit. Actigraphy data will be averaged across 7 days to create average sleep duration and sleep quality scores for each participant before and after intervention. We will then examine the relationship between changes in sleep variables and changes in insulin sensitivity assessed by the clamp study.

G. Summarize Knowledge to be Gained:

Achievement of these aims will yield the following *expected outcomes*: 1) sarcolemmal 1,2disaturated DAG and C18:0 ceramide promote insulin resistance through PKC and PP2A activation; 2) mitochondrial/ER sphingolipids correlate with mitochondrial function, ER stress, ROS, acyl-carnitine content, and insulin resistance; 3) DAG and sphingolipids reduce mitochondrial function and increase ROS and acyl-carnitine generation in vitro consistent with a cause and effect relationship. These outcomes will be *clinically significant* by identifying signaling pathways and mechanisms of accumulation of specific localized DAG and ceramide species which can ultimately be targeted for the prevention and treatment of diabetes.

H. References:

1. Adams JM, 2nd, Pratipanawatr T, Berria R, Wang E, DeFronzo RA, Sullards MC, Mandarino LJ: Ceramide content is increased in skeletal muscle from obese insulin-resistant humans. Diabetes 2004;53:25-31

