- Our long-term goal is to identify novel therapeutic targets to combat muscle insulin resistance and type 2 diabetes, filling a need not met by current therapies. The overall objective for this project is to determine the impact of changes in subcellular DAG and sphingolipid species on cell signaling and metabolic function, before and after insulin sensitizing lifestyle interventions. Our central hypothesis is that DAG and sphingolipids in muscle promote insulin resistance via mechanisms that are unique to location, type of lipid, and species. This hypothesis is based on extensive preliminary data (see Research Strategy -Approach), showing insulin resistance is related to sarcolemmal and mitochondrial/ER accumulation of specific DAG and sphingolipids. Our pilot studies revealed changes in specific localized species after an insulin sensitizing lifestyle intervention, and that DAG and sphingolipids alter mitochondrial function in vitro. We propose to measure skeletal muscle DAG and sphingolipid isomers, species, localization, and de novo synthesis before and after diet-induced weight loss or exercise training interventions in obese men and women. Comparing the two interventions will uncover differences in lipid localization, cellular signaling, and mechanisms for improvements in insulin sensitivity. Insulin sensitivity will be measured using hyperinsulinemic/euglycemic clamps, muscle lipids using LC/MS, and mitochondrial function using an Oroboros respirometer. The rationale underlying the proposed research is that elucidating changes in localized DAG and sphingolipids predicting insulin sensitivity will reveal specific localized lipids to target in therapeutics to prevent or treat type 2 diabetes.

To attain our overall objective, we propose three specific aims:

- 1. Identify the influence of sarcolemmal DAG and sphingolipids on cell signaling and insulin sensitivity before and after insulin sensitizing lifestyle interventions.
- Strong preliminary data shape our *working hypothesis* that sarcolemmal 1,2-disaturated DAG and C18:0 ceramide species will decrease after insulin sensitizing lifestyle interventions, leading to less PKC and PP2A activation, and enhanced insulin signaling.
- 2. Determine the impact of mitochondrial/ER DAG and sphingolipids on mitochondrial function and ER stress in vivo, before and after insulin sensitizing lifestyle interventions.

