The proposed studies will advance the field by identifying which subcellular membrane compartments of DAG and sphingolipids promote insulin resistance, and how these localized lipid species impact cell signaling and organelle function. *These novel contributions will be significant because they will reveal the key species and locations of DAG and sphingolipids, as well as mechanisms explaining accumulation that could be modified by insulin sensitizing therapeutic interventions.* Identifying specific localized DAG and sphingolipids species contributing to muscle insulin resistance will drive the field of lipid-induced insulin resistance forward in several ways. First, it will lay the foundation for more focused prevention and treatment therapies targeted to the localized DAG and sphingolipid content by identifying the extent to which de novo synthesis explains membrane accumulation. Third, this project will change the way pharmaceuticals are screened to reduce DAG and sphingolipids by focusing on changes in specific species and locations. This approach is expected to reveal novel therapeutic compounds that cannot be identified by focusing on whole cell content. Together, these advances will address an unmet clinical need to improve muscle insulin sensitivity, and reveal novel treatment and prevention strategies for diabetes.

III. Preliminary Studies/Progress Report: Preliminary Studies

We can fractionate muscle into multiple membrane compartments. We are uniquely suited for this project because we spent 3 years developing a method to separate frozen human skeletal muscle into fractions enriched in sarcolemma, mitochondria/ER, nuclear, and cytosolic compartments (Figure 1). This technique is a substantial advance, as the most recent studies only separate cytosol from mixed membranes, which cannot discriminate specific organelles containing lipids promoting insulin resistance. Lipids are then extracted from these fractions and analyzed using our lipidomic platform.

Calnexin (ER) VDAC (Mito) Lamin A/C (Nuc) Tubulin (Cyto) ADRP/PLIN2 (Lipid droplet)

Sarcolemmal 1,2-Disaturated DAG species relate

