to insulin resistance. The sum of all sarcolemmal disaturated 1,2-DAG species were significantly greater in T2D compared to lean volunteers (Figure 2A), and was inversely related to insulin sensitivity (Figure 2B). Notably, 1,3-disaturated DAG content was not different between groups revealing isomer specificity. We previously showed that membrane di-saturated DAG content predicted PKC activation and insulin resistance (26). These data agree and suggest that sarcolemmal DAG containing saturated acyl side chains represent membrane accumulation of DAG that is particularly negative for insulin sensitivity.

PKC ϵ activity is increased in obesity and T2D. We

measured the membrane/cytosol ratio of PKC ϵ , which is commonly used as a surrogate for PKC activity. We found significantly greater PKC ϵ activation in obese and T2D subjects compared to lean controls (Figure 3), with no significant differences found for PKC β II, δ , and θ isoforms. These data are consistent with greater PKC activation from sarcolemmal DAG accumulation.

Sarcolemmal C18:0 ceramide accumulates in insulin resistance. Of the 9 sarcolemmal ceramide species measured, only C18:0 ceramide was significantly greater in T2D compared to lean (Figure 4A), and was inversely related to the rate of glucose disappearance during an insulin clamp (Figure 4B). In a pilot study sarcolemmal C18:0 ceramide decreased by 21% after a combined weight loss

and exercise training intervention. These data parallel a recent publication by our lab showing C18:0 muscle ceramides significantly related to insulin resistance in a different cohort (27). C18:0 ceramide antagonizes an inhibitor of PP2A, resulting in increased PP2A activity (28). Combined, these data suggest that sarcolemmal C18:0 ceramide may promote insulin resistance, and due to the location may explain the canonical pathways of ceramide induced insulin resistance, including activation of PP2A activity, and inhibition of AKT phosphorylation in response to insulin.

Mitochondrial/ER ceramide accumulates in insulin

resistance. Mitochondrial ceramide content was greater in T2D compared to lean individuals, which is largely explained by C22:0 and C24:0 species (Figure 7A). Total ceramide content was inversely related to

insulin sensitivity (Figure 7B). These data are consistent with the hypothesis that mitochondrial ceramides promote insulin resistance.

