Exercise training and weight loss will differentially change DAG and sphingolipid content (11), revealing distinct changes in lipid localization, cellular signaling, metabolic function, and improvements in insulin sensitivity. We are expecting a 25% dropout rate, and are powered to complete testing on 17 individuals per group (51 total individuals). Subjects will be tested 48 hours after the last exercise bout to minimize acute exercise effects on insulin sensitivity. Women will be pre-menopausal and tested during the follicular phase (days 1-10) of the menstrual cycle to control for effects on insulin sensitivity.

Preliminary screening- Subjects will arrive after an overnight fast to the outpatient Clinical Translational Research Center (CTRC), and a fasting blood sample will be taken for a standard lipid panel, fasting glucose, TSH, and HbA1c. Women will take a pregnancy test. A physician will perform a history and physical, and subjects will fill out a dietary questionnaire, the NIH Dietary History Questionnaire II (DHQII), and the IPAQ physical activity questionnaire (33).

Strength and Exercise testing, body composition, maximal mitochondrial respiration, and MRI – Eligible subjects will undergo a Kin-Kom isokinetic dynamometer quadriceps strength test, Balke treadmill test to measure maximal work capacity (VO₂max) (34), a DEXA scan to determine body composition, a non-invasive test of maximal mitochondrial respiration, and MRI scan to measure leg muscle and fat mass, and liver fat content. During the maximal mitochondrial respiration test, volunteers will lie down on a table, and we will have a near infrared spectrometer measurement unit strapped to their leg. This unit uses a laser to measure the oxygen levels in the muscle. A blood pressure cuff will be wrapped around their upper thigh. To start the test, we will ask volunteers to make a muscle contraction for 20 seconds, after which we will intermittently inflate and deflate the blood pressure cuff every 5-10 seconds over a 5 minute period. This test will then be repeated. The total time for this test is 30 minutes.

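### Same-direction claims that a lipid effect is specific to a location, type or species have no direct test in the analysis plan, so they would rest on one result being significant and another not

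*Combined protocol and SAP*

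**What the plan says.** All references are to the combined protocol and SAP.

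- **Section I (Hypotheses and Specific Aims)** states the hypothesis of specificity: "DAG and sphingolipids in muscle promote insulin resistance via mechanisms that are unique to location, type of lipid, and species". **Section II (Background and Significance)** says the work will "reveal the key species and locations of DAG and sphingolipids".
- **Section IV.F (Data Analysis Plan), Aim 1:** "Correlations between the change in sarcolemmal DAG and sphingolipid species and the change in insulin sensitivity will be performed using Pearson's correlation coefficients". A one-way ANOVA with Tukey comparisons between the three arms follows, then Benjamini-Hochberg over changes in individual species, then principal components to group species. Aim 2 repeats this for the mitochondrial/ER fraction. On error control: "The type 1 error rate (alpha) will be set at 5% for all comparisons".
- **Section IV.A (Outcome Measures)** names the primary lipids: Di-C18:0 DAG and C18:0 ceramide in the sarcolemma, and total DAG and total ceramide in mitochondria/ER. Other localized lipids are exploratory.
- **Section III (Preliminary Studies)** shows how specificity has been inferred so far: "Notably, 1,3-disaturated DAG content was not different between groups revealing isomer specificity". It also singles out C18:0 as the only one of nine sarcolemmal ceramides to reach significance.

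**The concern.** To say that an effect belongs to one membrane, isomer or species and not to another is to claim a difference between them. Every comparison in section IV.F is either one lipid against insulin sensitivity (or, in Aim 2, against a mitochondrial or ER measure) or one arm against another. The two compartments sit in separate aims and are never brought together. Benjamini-Hochberg limits false positives among species, and principal components group them. Neither tests whether two lipids differ.

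The gap matters for these same-direction comparisons:

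- species within a class;
- 1,2- versus 1,3-disaturated DAG;
- sarcolemmal DAG versus sarcolemmal ceramide;
- ceramide in sarcolemma versus mitochondria/ER.

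For these, the planned output is a list of separate p-values. Lipids with identical true relations can fall on either side of 5% by chance. The intended product is a set of lipids and membranes to target in therapy, so a chance split could be carried forward as a target.

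**Working it through.** **Inputs.** n = 51 completers, 17 per arm (section IV.C); alpha 5% (section IV.F); r = -0.45 and r = -0.38 (section IV.F, Aim 1); nine ceramide species (section III). Sidedness is not stated. I take two-sided, because it reproduces the plan's power. The correlation between lipids is not given, so I assume 0.3 to 0.9 and show the range. Changes are simulated as multivariate normal.

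**Step 1: reproduce the plan's figure.** The plan says "With an overall n of 51, we will have 92% power to detect a Pearson correlation coefficient similar to our preliminary data". It takes that coefficient as -0.45, and it claims 80% at -0.38. Using Fisher's z, power = Φ(atanh|r| × √(n − 3) − 1.96).

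- r = 0.45: 0.4847 × √48 = 3.358; Φ(3.358 − 1.96) = 91.9% (stated 92%).
- r = 0.38: 0.4001 × √48 = 2.772; Φ(2.772 − 1.96) = 79.2% (stated 80%).

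Both reproduce.

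**Step 2: hand check.** Suppose lipids act identically, each test has power p, and the tests are independent.

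- Exactly one of two is significant with probability 2p(1 − p): 2 × 0.80 × 0.20 = 32%, or 2 × 0.92 × 0.08 = 15%.
- Nine give a mixed verdict with probability 1 − p⁹ − (1 − p)⁹: 87% at p = 0.80, and 53% at p = 0.92.

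Correlation between lipids lowers these figures.

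**Step 3: simulation with correlated lipids, all with the same true r.**

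| Inter-lipid correlation | 0.3 | 0.5 | 0.7 | 0.9 |
|---|---|---|---|---|
| Pair, exactly one significant, r = -0.38 | 28% | 23% | 18% | 11% |
| Pair, exactly one significant, r = -0.45 | 13% | 12% | 9% | 5% |
| Nine species, mixed after Benjamini-Hochberg, r = -0.38 | 72% | 56% | 37% | 13% |
| Nine species, mixed after Benjamini-Hochberg, r = -0.45 | 43% | 33% | 23% | 9% |
| Nine species, mixed, unadjusted, r = -0.38 | 73% | 62% | 48% | 28% |
| Nine species, mixed, unadjusted, r = -0.45 | 43% | 34% | 26% | 15% |

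Independent runs differ by about one percentage point. Both versions are shown for nine species because the plan ties Benjamini-Hochberg to changes in species and does not say whether it also covers the correlations.

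*Mixed* means some but not all significant. At r = -0.38, unadjusted, the pattern of exactly one in nine occurs in only about 0.4%, 1.2% and 2.7% of trials at inter-lipid correlations of 0.3, 0.5 and 0.7.

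**Step 4: the direct test.** Williams' t for two correlations sharing one variable, with n − 3 degrees of freedom:

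t = (r₁ − r₂) √{ (n − 1)(1 + r₁₂) / [ 2|R|(n − 1)/(n − 3) + r̄²(1 − r₁₂)³ ] }

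where |R| = 1 − r₁² − r₂² − r₁₂² + 2r₁r₂r₁₂ and r̄ = (r₁ + r₂)/2.

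- Equal true correlations: it rejects in about 5% of trials. Among pairs that split in Step 3, it confirms a difference in only about 13% to 19%.
- Power at inter-lipid correlation 0.3 to 0.7: 82% to 99.8% for 0.45 versus 0; 61% to 94% for 0.45 versus 0.10; 37% to 70% for 0.45 versus 0.20.

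**Step 5: arm differences.** The same logic applies to nine species tested by Tukey at 17 per arm, but the rate depends on an effect size that the plan does not fix. The stated 84.6% power implies a fall of about 1.2 SD, where nine equal species give a mixed verdict in roughly 60% to 40% of trials at inter-lipid correlation 0.3 to 0.7. The pilot figures read literally, 0.041/0.02 = 2.05 SD, give under 1%. I therefore rest the point on the correlations.

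**The case against.** A reader might infer that specificity could be shown only through a significant result beside a non-significant one. The documents do not support that.

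- **Opposite directions.** Section I predicts that sarcolemmal disaturated DAG falls while mitochondrial/ER DAG rises, and that mitochondrial/ER sphingolipids fall while DAG there rises. Two significant results of opposite sign would be sound evidence on those contrasts.
- **Aim 3.** Section IV.C applies ceramide, dihydroceramide, 1,2-DAG and 1,3-DAG to muscle fibres beside vehicle and a triolein control. That is an experimental route to type and isomer. It uses mixtures, so it cannot separate species, and section IV.F gives no analysis for it.
- **Mechanism.** The hypothesis concerns mechanisms, and two lipids with equal correlations could act by different pathways. This stands: the contrasts proposed below test association and response, not the PKC, PP2A or mitochondrial pathways.
- **No stated rule.** The isomer and C18:0 inferences concern preliminary data, and nothing in section IV.F says that a null result means specificity. True, but section IV.F supplies no other basis for same-direction claims.
- **Size.** Most of the nine species are exploratory. At the plan's own r = -0.45 a pair splits fairly seldom. Many mixed verdicts have seven or eight of nine significant. All of this stands and limits how strongly the point can be put.

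**Conclusion.** The point holds for same-direction comparisons. For these the plan has no test of a difference, and separate p-values would sometimes separate lipids that act alike: about 28% to 11% of trials for a pair at r = -0.38, and 13% to 5–6% at r = -0.45. For nine equal species after Benjamini-Hochberg, the mixed-verdict rates are about 72% to 13% and 43% to 9%. A direct test holds the error at about 5%.

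These figures assume 51 completers, two-sided tests, normal data, and inter-lipid correlations of 0.3 to 0.9, which the documents do not give. The low ends apply when lipids are nearly collinear.

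It would go too far to conclude that all specificity claims are unsupported, or that a lone false species will commonly emerge from nine. The first fails on the opposite-direction contrasts and Aim 3. The second pattern is rare, at about 3% or less unadjusted. This is a cheap improvement, not a flaw that undermines the trial.

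**What to change.** In section IV.F, Aims 1 and 2, prespecify a short list of direct contrasts led by the primary lipids.

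1. **Relation to insulin sensitivity.** Use Williams or Steiger tests, or a participant bootstrap of the difference in correlations, for:
   - C18:0 ceramide versus the mean of the other sarcolemmal ceramides;
   - 1,2- versus 1,3-disaturated DAG;
   - sarcolemmal versus mitochondrial/ER ceramide;
   - sarcolemmal versus mitochondrial/ER DAG.

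   For the two location contrasts, use the same measure in both compartments, because the primary outcomes are single species in the sarcolemma and totals in mitochondria/ER.
2. **Response to intervention.** Add arm-by-compartment and arm-by-species contrasts on within-person log changes.
3. **Reporting.** Give each difference with its confidence interval. Use *specific* or *unique* only where the contrast supports it. Report non-significant lipids with their intervals, not as unrelated.

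The cost is analysis-plan text and a little code. The fractions come from the same biopsies, and no procedure or sample size changes. The downside is that fewer specificity claims will be supported, and power for partial differences is limited (37% to 70% for 0.45 versus 0.20). That is a reason to rely on the intervals.

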Mitochondrial/ER ceramides decrease after insulin sensitizing lifestyle intervention - Pilot data for a combined weight loss/exercise training intervention show decreased whole cell ceramide content, as shown before (11; 15) (Figure 8). However, the decrease in whole cell ceramide content comes only from a decrease in mitochondrial/ER ceramide. These data point to an important role of mitochondrial/ER ceramides on insulin sensitivity in vivo.

Mitochondrial/ER DAG accumulates in lean insulin sensitive individuals. Preliminary data show mitochondrial/ER 1,2- and 1,3-DAG were

Figure 2. Sarcolemmal di-saturated DAG content by group (A), and by insulin sensitivity (B) in lean, obese, and type 2 diabetics. Values are means +/- SEMC # significantly different than lean, p<0.05.

Figure 3. PKCE activation in lean, obese, and type 2 diabetics. Values are means +/- SEM. #= significantly different than lean, p<0.05.

Figure 4. Sarcolemmal C18:0 ceramide content by group (A), and by insulin sensitivity (B) in lean, obese, and type 2 diabetics. Values are means +/- SEM. #= significantly

different than lean, p < 0.05.

higher in lean individuals compared to obese or type 2 diabetic volunteers (Figure 9), with the greater DAG content distributed over most species. These data are counterintuitive, but may reflect the greater content of mitochondria in lean individuals compared to obese volunteers with and without diabetes, and/or increased mitochondrial fission/fusion (29; 30).

Mitochondrial/ER DAG increase after weight loss and exercise training.

Preliminary data from a weight loss and exercise training intervention show an increase in mitochondrial/ER 1,2-DAG after the intervention (Figure 10). These data are consistent with some reports in the literature where DAG concentration was increased in endurance trained athletes (13). These data agree with Figure 9 and suggest mitochondrial/ER DAG accumulation may be a previously unrecognized adaptation to exercise training and/or weight loss.

Insulin resistant muscle accumulates long chain acyl-carnitines and shows oxidative

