stress. Basal acyl-carnitines revealed accumulation of many long chain acyl-CoA's in type 2 diabetics including C18:0, C18:2-OH, and C20:4, which are thought to promote insulin resistance (Figure 11A). A significantly decreased GSH/GSSG ratio in type 2 diabetes individuals compared to lean volunteers suggest a more oxidized state, consistent with increased oxidative stress in insulin resistance (Figure 11B).

DAG and ceramide decrease mitochondrial

function. We administered 1,2-DAG, ceramide, dihydroceramide, and vehicle controls to isolated rat mitochondria in vitro to evaluate the impact on mitochondrial respiration using pyruvate and malate as substrates. DAG and ceramide decreased state 3 respiration, with no changes observed with dihydroceramide administration (Figure 12A and B). State 4 respiration did not change for 1,2-DAG and dihydroceramide, but increased significantly with increasing doses of ceramide. Both 1.2-DAG and ceramide decreased ADP/O ratios (Figure 13A and B), while dihydroceramide had no effect. These data indicate 1.2-DAG and ceramide reduced mitochondrial respiration and coupling, and are consistent with accumulation of mitochondrial lipids altering mitochondrial function.

Protocol Template CF-146, Effective 7/10/11

IV. Research Methods

A. Outcome Measure(s):

Primary outcomes:

Aim 1: Change in insulin sensitivity, change in sarcolemmal Di-C18:0 DAG and C18:0 ceramide, change in PKCepsilon and PP2A activity

Aim 2: Change in insulin sensitivity, change in mitochondrial/ER total DAG and ceramide content, change in state 3 mitochondrial respiration, change in GSH/GSSG, change in C18:0, C18:2-OH, and C20:4 acylcarnitines, change in GRP78

Aim 3: Change in mitochondrial state 3 and state 4 respiration in response to DAG and ceramide before and after lifestyle interventions

Secondary outcomes: Changes in other localized lipids and intracellular responses will be exploratory in nature. In addition, we will collect subjective and objective information about sleep and an exploratory analysis.

B. Description of Population to be Enrolled:

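### The Aim 1 DAG primary is a single species with no isomer (Di-C18:0), while the hypothesis names 1,2-disaturated DAG and the correlation behind the 92% power is for the sum of those species

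*Combined protocol and SAP*

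**What the plan says.** **Hypothesis.** Section I (Hypotheses and Specific Aims, Aim 1) expects that "sarcolemmal 1,2-disaturated DAG and C18:0 ceramide species will decrease after insulin sensitizing lifestyle interventions". For DAG this is a class with its isomer named. Section IV.G (Summarize Knowledge to be Gained) words the expected Aim 1 conclusion for the same class.

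**Evidence.** Section III (Preliminary Studies) reports: "The sum of all sarcolemmal disaturated 1,2-DAG species were significantly greater in T2D compared to lean volunteers". It adds that this sum was inversely related to insulin sensitivity (Figure 2B). On the other isomer it says that "1,3-disaturated DAG content was not different between groups revealing isomer specificity".

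**Primary outcome.** Section IV.A (Outcome Measure(s)) lists for Aim 1 the "change in sarcolemmal Di-C18:0 DAG and C18:0 ceramide", with insulin sensitivity, PKCepsilon and PP2A activity. Of everything else it says: "Changes in other localized lipids and intracellular responses will be exploratory in nature".

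**Power.** Section IV.F (Data Analysis Plan, Aim 1) has two statements.
- With n = 51 there is 92% power for a correlation "similar to our preliminary data (Figure 2B, r= -0.45" in value, and 80% power down to -0.38.
- With 17 per group there is 84.6% power under Tukey's procedure. The input is a pilot change in sarcolemmal C18:0 ceramide, and the result is then extended to sarcolemmal DAG and sphingolipids together.

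**The concern.** The DAG quantity that carries the hypothesis, the evidence and the correlation power is not the DAG quantity listed as primary.

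Two things follow. First, the result on Di-C18:0 would not settle the hypothesis either way. A null result on one species leaves the class untested, and a positive result on one species, of an isomer chosen later, does not establish the class claim in Section IV.G. Second, a reader of Section IV.F will take 92% as the power for the Aim 1 DAG correlation, although its effect size belongs to another variable.

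The missing isomer adds an open choice. The plan's own data show a group difference for the 1,2 form and none for the 1,3 form, so it matters which one is analysed.

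**Working it through.** **Step 1. The places side by side, for DAG only**

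| Place | DAG quantity |
|---|---|
| Section I, Aim 1 hypothesis | 1,2-disaturated DAG (class; no sum mentioned) |
| Section III, Figure 2A and 2B | sum of disaturated 1,2-DAG species |
| Section IV.F, r = -0.45 | Figure 2B, hence that sum |
| Section IV.G, expected conclusion | 1,2-disaturated DAG (class) |
| Section IV.A, primary outcome | Di-C18:0 only, no isomer |

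The sum is not on the primary list, so it falls under the exploratory outcomes. The ceramide side is consistent: Section III reports that C18:0 was the only one of 9 sarcolemmal ceramide species that was higher in T2D than in lean volunteers, and C18:0 ceramide is the primary. The text gives no comparable result for Di-C18:0 DAG. Aim 2 makes total DAG and ceramide content primary, so an aggregate outcome is a form that the plan already uses.

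**Step 2. Is Di-C18:0 specific to one isomer?** No. In the in vitro work for Aim 3 (Section IV.C), Di-C18:0 is a component of both the 1,2- and the 1,3-DAG mixes. The muscle biopsy paragraph says the assay separates the isomers. Both will be available, and the outcome label does not choose.

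**Step 3. Reproduce the plan's power.** Inputs from Section IV.F: n = 51, alpha 5%, r = -0.45 and -0.38. Sidedness is not stated; two-sided is taken because it reproduces the figure (one-sided gives 95.7% at 0.45).

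Power = Φ(atanh|r| × √(n − 3) − 1.960), with √48 = 6.928.
- r = 0.45: 0.4847 × 6.928 = 3.358; less 1.960 = 1.398; power **91.9%** (stated 92%).
- r = 0.38: 0.4001 × 6.928 = 2.772; less 1.960 = 0.812; power **79.2%**, or 79.9% with bias correction (stated 80%).

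The arithmetic is sound. Solving for 80% power: (1.960 + 0.842) / 6.928 = 0.404, and tanh(0.404) = 0.384. This agrees with the plan's 0.38.

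**Step 4. Power for Di-C18:0.** The text gives no correlation, change or SD for this species, so no single figure can be computed. Over assumed true values of r (size), with n = 51 and two-sided 5%:

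| Assumed r | Power |
|---|---|
| 0.50 | 97% |
| 0.45 | 92% |
| 0.40 | 84% |
| 0.35 | 72% |
| 0.30 | 57% |
| 0.25 | 42% |
| 0.20 | 29% |

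The first row is 0.5493 × 6.928 − 1.960 = 1.846, and Φ(1.846) = 0.968.

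**Step 5. What kind of correlation is -0.45?** The Figure 2 caption reads "Sarcolemmal di-saturated DAG content by group (A), and by insulin sensitivity (B) in lean, obese, and type 2 diabetics". It is cross-sectional and spans three groups. The planned test correlates changes with changes within an obese trial sample. So -0.45 is not an estimate for change scores, whichever DAG variable is used.

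**The case against.** The strongest reply has four parts.

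1. **A single species fits the plan's logic.** The central hypothesis is that mechanisms depend on location, lipid type and species. Di-C18:0 is a disaturated DAG and so, if 1,2, a member of the hypothesised class. The hypothesis itself does not mention a sum. This stands as a reason to report Di-C18:0. It does not make one member a test of the class, and the text offers no result that singles it out as the ceramide data single out C18:0.

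2. **The 92% is not wrong.** Power at a given r and n holds for any pair of variables with that true r, and the 80% at -0.38 already tells a reader what Di-C18:0 must reach. This stands in full. A reader might infer that the true power is well below 92%. For example, if Di-C18:0 related to insulin sensitivity only through the sum and correlated with it at 0.9, 0.8, 0.7 or 0.6, r would be 0.405, 0.36, 0.315 or 0.27, and power 85%, 74%, 62% or 48%. That model can only shrink r. The documents give no species-to-sum correlation, and one species can track insulin sensitivity better than a sum does.

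3. **The isomer is a labelling gap.** Nothing says that the isomers will be pooled, and the hypothesis names 1,2. This stands: a reader might infer that the 1,3 form will be mixed in, but the plan does not say so. Naming the isomer would cure that part and leave the species-versus-class mismatch.

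4. **Changing the primary does not validate 92%.** Because of Step 5 this also stands. The text also gives no pilot change or SD for the sarcolemmal DAG sum, so the DAG group comparison has no DAG-specific power input under either choice.

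**Conclusion.** The mismatch is real and confined to DAG in Aim 1. The hypothesis and intended conclusion concern sarcolemmal 1,2-disaturated DAG, the correlation used for power is for the sum of those species, and the listed primary is one species with no isomer. No Aim 1 power statement uses Di-C18:0 data.

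Its size cannot be given as a single loss of power. The 92% is correct for a true r of -0.45 at n = 51, and the text does not support that r for Di-C18:0. Power for that species is unknown: at least 80% if its correlation is about 0.38 or more in size, lower otherwise, and above 92% if it exceeds 0.45.

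A reader might go further and conclude that Aim 1 as a whole is powered on something other than its primaries. The documents do not support that. The 84.6% statement takes its input from C18:0 ceramide, which is a listed primary. Whether that figure follows from its printed inputs is a separate question.

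The verdict rests on the text alone. The figure panels could not be read, so a species-level DAG result inside them cannot be excluded. Two-sided testing is assumed in the power check.

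**What to change.** Before any lipid outcome is analysed, with the change dated:

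- In Section IV.A, make the Aim 1 DAG primary the change in the sum of sarcolemmal 1,2-disaturated DAG species.
- Report 1,2-Di-C18:0 DAG, with the isomer named, among the individual species that Section IV.F already handles by Benjamini-Hochberg.
- In Section IV.F, state that r = -0.45 is a cross-sectional estimate for the sum across lean, obese and T2D participants, that it is not an estimate for Di-C18:0 or for change scores, and that 92% is conditional on it.

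The cost is small. The planned LC/MS analysis already yields the species and isomers, so samples, assays and n are unchanged. The downside is that a named primary species becomes secondary. The change aligns the primary result with the claim the trial intends to make; it does not by itself secure 92% power.
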